Statistical Analyses. A two-sided P value of 0·05 will be used to calibrate the significance and false discovery rate. For the primary and key secondary endpoints, we will employ a Benjamini-Hochberg step-down procedure to adjust for the multiple comparisons across 5 outcome scores (HSCL-25, WHODAS 2·0, PoC-OP, CAT-MH depression, and CAT-MH anxiety) at 2 follow-up points (months 6 and 12). If the lowest of the ten P values was less than 0·005 (0·05 ÷ 10), it will be considered to be significant; the second lowest P value will be considered to be significant if less than 0·0056 (0·05 ÷ 9); the third lowest P value will be significant if less than 0·006 (0·05 ÷ 8); and so on. Primary and key secondary efficacy endpoints will be separately analyzed using a general linear model to estimate the treatment effect. Except for PoC-OP, baseline outcome scores will be included as covariates in all analyses. Site (Massachusetts versus North Carolina) will also be included as covariate in all analyses. This general linear model has the following form:

$$y_{i,post-baseline} = \alpha_0 + \alpha_1 Intervention_i + \alpha_2 y_{i,baseline} + \alpha_3 site_i + \varepsilon_i$$

where $y_{i,post-baseline}$ represents an outcome measure for participant i at either 6- or 12-months post-baseline. $Intervention_i$ will be an effect-coded variable equal to -0.5 if participant i was randomized to the control group and equal to 0.5 if participant i was randomized to the intervention group. $y_{i,baseline}$ is the baseline measure of the outcome (except for PoC-OP), $site_i$ is a binary indicator equal to one if participant i was recruited in Massachusetts and equal to 0 if recruited in North Carolina, and ε_i is an error term. Because participants will be recruited in multiple CBOs/clinics across the two sites, in sensitivity analyses we will use generalized linear mixed models with a random intercept accounting for clustering within CBOs/clinics for each primary and key secondary effectiveness endpoint.

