The target sample size was designed to achieve adequate power for our research questions. Using data from prior studies on the effectiveness of similar interventions, the estimated effect size for the outcomes ranged from 0·24 to 0·68. The nonparticipation rate of enrolled participants was assumed to be 13%. Our sample size of 1,200 (600 treatment and 600 control) from North Carolina and Massachusetts is thus effectively 1044. This sample yielded 87% power to detect an intervention effect size of 0·20, with a two-sided significance level of 0·05. Testing whether there is a differential effect of Strong Minds-Strong Communities based on participants' race and ethnicity means trying to determine whether race and ethnicity moderated the impact of the intervention. The racial and ethnic composition of our sample was roughly 63% Latinx, 14% non-Latinx Black, 13% Asian, 9% White, and 1% other races or ethnicities. Assuming a large effect size of the intervention for White participants ($> 0\cdot5$), a small effect size for Black participants ($< 0\cdot3$), and a medium effect size for Asian and Latinx participants ($> 0\cdot3$ and $< 0\cdot5$), we will have 80% power to detect a significant intervention effect in each racial and ethnic group with a sample size of 1044. Similarly, testing whether there is a differential effect of Strong Minds-Strong Communities in North Carolina compared to Massachusetts means testing whether site moderated the impact of the intervention.

VIII. Risks and Discomforts

A. Psychosocial (non-medical) risks:

The safety of intervention participants will be closely monitored during the Strong Minds-Strong Communities intervention. Participants will be administered the PHQ-9 depression screener and the GAD-7 anxiety screener during research interviews and biweekly during intervention sessions, and in biweekly check-ins for usual care participants. If participants endorse the Item

9 suicidality question of the PHQ-9, they will be administered the Paykel Suicidality Screener.

Those who endorse questions 4 and 5 of the Paykel, suggesting active suicidality, will be provided emergency care following emergency protocol developed by the research team.

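### The stated 87% power does not follow from its own inputs: 1,044 participants, effect size 0.20 and two-sided 0.05 give about 90%

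*Combined protocol and SAP*

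**What the plan says.** The power paragraph (section VII.C, Power Analysis) gives every input that a two-arm comparison of means needs:

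- Randomised sample and allocation: "Our sample size of 1,200 (600 treatment and 600 control").
- Loss: "The nonparticipation rate of enrolled participants was assumed to be 13" per cent.
- Sample after loss: "from North Carolina and Massachusetts is thus effectively 1044".
- Effect size and level: "to detect an intervention effect size of 0·20", "with a two-sided significance level of 0·05".
- Result: "This sample yielded 87% power to detect an intervention effect size of" 0.20.

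The same paragraph uses 1,044 again for its claim of 80% power within each racial and ethnic group.

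Two features of the analysis plan (section VII.A, Statistical Analyses) could bear on the figure, but the power paragraph mentions neither. Clustering is handled only outside the main model: "in sensitivity analyses we will use generalized linear mixed models with a random intercept accounting for clustering within CBOs/clinics". Baseline adjustment is part of the main model: "Except for PoC-OP, baseline outcome scores will be included as covariates in all analyses". The documents give no intraclass correlation, cluster size, design effect or baseline correlation.

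**The concern.** This is the trial's main power statement, and a reader should be able to reproduce it from the paragraph that contains it. Here the reader gets about 90%. Either the printed percentage is wrong, or something that lowers the power was used and left out.

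The second possibility has a consequence within the paragraph. If an unprinted factor reduces the information below 1,044 participants, then 1,044 is not the effective sample size, and the by-group sentence that reuses it rests on the wrong number. The total sample size is not at stake, because the stated power is lower than the computed one.

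**Working it through.** **Inputs, all from section VII.C.** 1,200 randomised 1:1; 13% loss; effect size 0.20; two-sided 0.05. Two assumptions are needed: 0.20 is a standardised mean difference (no SD is given), and loss is equal in the two arms.

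**Step 1: the sample after loss.** 1,200 × (1 − 0.13) = 1,044, or 522 per arm. This agrees with the plan.

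**Step 2: the power.** Power = Φ(d / √(2/n) − 1.960), with n per arm.

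- √(2/522) = 0.0619
- 0.20 / 0.0619 = 3.231
- Φ(3.231 − 1.960) = Φ(1.271) = 0.898

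The noncentral t also gives 89.8%. The plan's 87% is not reproduced; the difference is 89.8 − 87 = 2.8 points.

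**Step 3: other readings of the stated inputs.**

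| Reading | Power |
|---|---|
| No loss, 1,200 | 93.4% |
| Loss applied as 1,200/1.13 = 1,062 | 90.3% |
| One-sided 0.05 at 1,044 | 94.4% |
| All 156 losses in one arm (600 vs 444) | 89.1% |
| 13% lost from one arm only (522 vs 600) | 91.6% |
| Baseline correlation 0.3 (assumed) at 1,044 | 92.3% |
| Baseline correlation 0.5 (assumed) at 1,044 | 96.2% |
| Effect diluted by 13%, at 1,200 | 85.4% |
| Effect diluted by 13%, at 1,044 | 80.3% |
| Level 0.005 (first step of the multiplicity rule) at 1,044 | 66.4% |

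None gives 87%. The nearest from below, 85.4%, does not use the 1,044 that the sentence names.

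**Step 4: what would give 87%.**

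- Smaller effective sample: n per arm = 2 × (1.960 + 1.126)² / 0.20² = 476.2, so 477 per arm or 954 in total. That is a loss of 1 − 954/1,200 = 20.5%. Power rounds to 87% for totals from about 940 to 968, a loss of about 22% to 19%.
- Variance inflation at 1,044: 1,044 / 954 = 1.094.
- Smaller effect at 1,044: (1.960 + 1.126) × √(4/1,044) = 0.191.

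The documents state none of these. 87% is also the retention rate (100% − 13%), so it may have been carried over by mistake.

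**Step 5: why the effective size matters for the by-group sentence.** The paragraph puts Asian participants at 13% of the sample and assumes for them an effect above 0.3 and below 0.5. With equal arms, the effect detectable with 80% power is (1.960 + 0.842) × √(4/N).

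- N = 0.13 × 1,044 = 135.7: 2.802 × 0.1717 = 0.481
- N = 0.13 × 954 = 124.0: 2.802 × 0.1796 = 0.503

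The first lies just inside the assumed band and the second just outside it. The second applies only if the effective size really is about 954.

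**The case against.** The strongest defence is that 87% may come from one coherent calculation with an input left out. The plan recognises clustering within CBOs/clinics, and a design effect of about 1.09 would be modest. With 20 participants per cluster and an intraclass correlation of 0.005 (both assumed), it is 1 + 19 × 0.005 = 1.095. This stands as a possibility. A reader might infer that the power and loss figures cannot belong to one calculation, and the documents do not support that. Equally, nothing in them says that a design effect was used, and the 1,044 is derived from nonparticipation alone.

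A reader might also infer that the true planning basis was 20% loss and 960 evaluable, because 960 gives 87.3%. On that reading planned missing data would be understated and the evaluable sample overstated. The documents do not support this either. Neither 20% nor 960 appears anywhere, the match is solved backwards from 87%, and a range of totals fits equally well. The step from 1,200 to 1,044 is correct, and 1,044 is used twice.

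The last objection concerns weight, and it stands. The plan claims less power than its inputs deliver. At 0.24, the low end of the effect sizes it cites, 1,044 gives Φ(0.24/0.0619 − 1.960) = Φ(1.917), about 97%. Baseline adjustment, planned for every outcome except PoC-OP, would raise power further.

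**Conclusion.** The figure is wrong as written. The stated inputs give about 90% power (89.8%), not 87%. This rests on reading 0.20 as a standardised difference, on equal loss in both arms, and on no covariate adjustment or design effect, since none is stated. The documents cannot show whether 87% is a slip or reflects an omitted assumption, and no particular loss rate or design effect should be attributed to the sponsor. The understatement is 2.8 points and conservative. It changes neither enrolment nor the primary analysis, so the point is minor.

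**What to change.** Make the paragraph reproducible in one of two ways.

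1. If nothing was left out, replace 87% by about 90%, keep 13% and 1,044, and note that the calculation uses no covariate adjustment or design effect.
2. If 87% came from an assumption that is not printed, such as a design effect of about 1.09 for clustering within CBOs/clinics or a higher loss rate, state that assumption and the resulting effective sample size. Then use the same size in the by-group power sentence and check that its 80% claim still holds.

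Either way the cost is rewording one paragraph, with no change to enrolment or the analysis.

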Data will be collected at several points. All potential participants will complete a 20-30-minute screener to determine eligibility. Eligible participants will then complete a baseline assessment, as well as follow-up assessments at 3, 6 and 12 months post-baseline. In addition, all participants will complete a biweekly symptom assessment, using the PHQ-9 and GAD-7, and the Paykel Suicide Screener, if necessary.

VII. Biostatistical Analysis

A. Specific data variables being collected for the study (e.g. data collection sheets).

Screener, Baseline Assessment, Follow-up Assessment, Symptom Assessment (PHQ-9 and GAD-7)

The proposed study has four goals:

- 1) To test the effectiveness of an evidence-based, CHW-led mental health intervention, The Strong Minds-Strong Communities Randomized Clinical Trial (RCT), focused on (1)

decreasing depression and anxiety symptoms, (2) improving functioning, and (3) increasing perceived quality of care among low-income racial, ethnic, and linguistic minorities.

- 2) To test whether there is a differential effect of Strong Minds-Strong Communities based on participants' race and ethnicity, thereby identifying whether the intervention can be particularly effective for certain racial and ethnic groups.
- 3) To test whether there is a differential effect of Strong Minds-Strong Communities based on participants' language, thereby identifying whether the intervention can be particularly effective for certain linguistic groups.
- 4) To test whether there is a differential effect of Strong Minds-Strong Communities in North Carolina compared to Massachusetts, thereby identifying whether the effectiveness of the intervention is associated with a specific geographic location.

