Prespecified subgroup analyses of the primary and key secondary endpoints will be performed for participant's self-identified race and ethnicity (non-Hispanic White, non-Hispanic Black, Asian, and Hispanic or Latino), language (English, Spanish, Mandarin, and Cantonese), and site (Massachusetts and North Carolina). Subgroup differences will be tested in three omnibus interaction tests. These three interactions will be examined for 5 outcome scores (HSCL-25, WHODAS 2·0, PoC-OP, CAT-MH anxiety, and CAT-MH depression) at month 6 and month 12, which will result in 30 statistical tests ($3 \times 5 \times 2$). No adjustment for the multiple comparisons will be made, and about two statistically significant interaction tests ($P < 0.05$) are expected on the basis of chance alone.

Change from baseline in HSCL-25, WHODAS 2·0, PoC-OP, CAT-MH depression, and CAT-MH anxiety scores at the exploratory endpoint at month 3, and exploratory subgroup analyses based on participant's baseline severity of depression and anxiety will similarly be analyzed using a general linear model which included baseline scores (except for PoC-OP) and site as covariates.

B. Missing data

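### The claimed 80% power in each racial and ethnic group does not follow from the plan's own figures: for Black participants it is at most about 44% unadjusted, and no power is given for the interaction test that answers Goal 2

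*Combined protocol and SAP*

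**What the plan says.** Section VII.C Power Analysis takes 1,200 enrolled participants, allows 13% nonparticipation, and works with 1044. For the overall comparison it says "This sample yielded 87% power to detect an intervention effect size of" 0.20, two-sided at 0.05. On prior evidence it says "Using data from prior studies on the effectiveness of similar interventions, the estimated effect size for the outcomes ranged from" 0.24 to 0.68.

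It then turns to race and ethnicity. The composition is "roughly 63% Latinx, 14% non-Latinx Black, 13% Asian, 9% White, and 1% other races or ethnicities". The assumed effects are above 0.5 for White participants, "a small effect size for Black participants" (below 0.3), and between 0.3 and 0.5 for Asian and Latinx participants. From these it concludes that "we will have 80% power to detect a significant intervention effect in each racial and ethnic group with a sample size of 1044".

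Section VII lists the differential effect by race and ethnicity as Goal 2, "thereby identifying whether the intervention can be particularly effective for certain racial and ethnic groups". The paragraph on prespecified subgroup analyses says how this is examined: "Subgroup differences will be tested in three omnibus interaction tests". On covariates, the Statistical Analyses paragraph says: "Except for PoC-OP, baseline outcome scores will be included as covariates in all analyses". No baseline-to-outcome correlation appears anywhere in the document.

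**The concern.** The smallest assumed effect is paired with one of the small groups, yet the plan claims the same 80% there as elsewhere. With 14% of 1044 and an effect below 0.3, that is implausible on sight.

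The sentence also answers a different question from the one it introduces. Power to find an effect within each group is not power to find that the effects differ between groups, and Goal 2 asks about the difference.

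What is at stake is how null results are read. If the true effect in Black participants were 0.30, an unadjusted test in that group would miss it about 56% of the time (100 − 44), not the 20% that the stated power implies. A reader who trusts the 80% would give a null result in this group too much weight. The same reader has no figure at all for judging a non-significant interaction.

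**Working it through.** **Inputs.** From section VII.C: effective N = 1044, 1:1 allocation, two-sided 0.05, and the group shares and effect ranges quoted above. I assume 1:1 allocation within each group. Correlations r between baseline and outcome are my assumptions.

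**Formulas.** With n per arm and standardised effect d:

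- Power = Φ( d/√(1−r²) · √(n/2) − 1.96 ), with r = 0 for an unadjusted analysis.
- Effect detectable with 80% power = 2.80 · √(2/n) · √(1−r²).

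**The plan's overall figure first.** n = 522 and d = 0.20: 0.20 · √261 = 3.23, and Φ(3.23 − 1.96) = 89.8%. The plan states 87%, which is slightly conservative. Crediting baseline adjustment would push the figure above 89.8%, so the stated value shows no sign of it.

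**Within-group effects detectable with 80% power**, n per arm = 1044 × share / 2:

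| Group | n per arm | Plan's assumed d | r = 0 | r = 0.5 | r = 0.7 |
|---|---|---|---|---|---|
| Latinx | 329 | 0.3 to 0.5 | 0.22 | 0.19 | 0.16 |
| Black | 73 | below 0.3 | 0.46 | 0.40 | 0.33 |
| Asian | 68 | 0.3 to 0.5 | 0.48 | 0.42 | 0.34 |
| White | 47 | above 0.5 | 0.58 | 0.50 | 0.41 |

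**Black participants.** At d = 0.30 and r = 0: 0.30 · √(73.08/2) = 1.81, and Φ(1.81 − 1.96) = 44.2% (43.7% by the noncentral t). This is the ceiling of the assumed range.

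| d | r = 0 | r = 0.5 | r = 0.7 | r needed for 80% |
|---|---|---|---|---|
| 0.30 | 44% | 55% | 72% | 0.76 |
| 0.24 | 31% | 39% | 53% | 0.86 |
| 0.20 | 23% | 29% | 40% | 0.90 |

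The last column is √(1 − (d/0.463)²). Without adjustment, 80% at d = 0.30 needs 2 · (2.80/0.30)² ≈ 174 per arm, about 349 Black participants, or 349/0.14 ≈ 2,490 in total.

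**Other readings, d = 0.30, Black participants, unadjusted.** One-sided 0.05 gives 56.7%; N = 1200 with no dropout gives 49.4%; four equal-sized groups give 67.8%. None reaches 80%.

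**Other groups, unadjusted.** Latinx: 97% at 0.30. Asian: 42% at 0.30, 64% at 0.40, 83% at 0.50. White: 68% at 0.50, 83% at 0.60.

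**Omnibus interaction (3 df).** Noncentrality = Σ N_g (d_g − weighted mean)² / (4(1−r²)), critical value 7.81. The point effects are illustrative choices.

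| Latinx / Black / Asian / White | r = 0 | r = 0.5 |
|---|---|---|
| 0.4 / 0.3 / 0.4 / 0.5 | 9% | 10% |
| 0.4 / 0.2 / 0.4 / 0.6 | 22% | 29% |
| 0.4 / 0.2 / 0.4 / 0.8 | 46% | 59% |
| 0.5 / 0 / 0.5 / 0.8 (extreme) | 79% | 90% |

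If group effects are held within both the group ranges and 0.24 to 0.68, the maximum is at 0.3 / 0.24 / 0.5 / 0.68: 37% unadjusted, 48% at r = 0.5, 67% at r = 0.7. The plan gives 0.24 to 0.68 for outcomes, so applying it to groups is an assumption.

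**Site interaction.** With 1044/4 = 261 per site and arm, the detectable difference in effect is 2.80 · √(4/261) = 0.35, or 0.35 · √0.75 = 0.30 at r = 0.5.

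**The case against.** The strongest reply is baseline adjustment. Four of the five outcomes are analysed with the baseline score in the model, so unadjusted figures are the least favourable case; at d = 0.30 the miss rate in Black participants falls from 56% to 45% at r = 0.5 and 28% at r = 0.7. That is fair, but it does not restore 80%: the correlation would have to be at least 0.76, and higher for any effect below 0.30. The plan states none, and PoC-OP, a primary outcome, has no baseline covariate. The comparison of 87% with 89.8% is only suggestive, since the plan does not say how either of its power figures was obtained.

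Second, the plan gives ranges, not points. White effects have no upper limit and Asian effects may lie near 0.5, so the stated ranges can satisfy the claim for those two groups. This stands: for them the sentence is underspecified rather than wrong. Only the Black group fails across its whole unadjusted range.

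Third, the interaction figures depend on chosen effects and run from 9% to 79% unadjusted. That also stands. They show the order of magnitude and should always appear with their assumptions. The plan's caution that about two interaction tests may be significant by chance concerns false positives and does not address low power.

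Finally, the overall power statement and primary analysis are unaffected. That is true, and it limits the consequence to Goal 2 and how its results are read.

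**Conclusion.** The concern holds. The claim of 80% power in every group is contradicted by the plan's own share and effect size for Black participants, where unadjusted power is at most about 44%. It could be rescued only by a correlation of about 0.76 or more, which the plan does not state and which could not apply to PoC-OP. The claim is true for Latinx participants and conditional for Asian and White participants. Separately, the plan gives no power for the interaction test that addresses Goal 2.

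The Black-group result rests only on the plan's figures, equal allocation within the group and the standard two-sample formula. The adjusted and interaction figures rest on assumed correlations and effects. Confidence is high. This should be fixed, but it does not threaten the primary comparison.

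**What to change.** In section VII.C, delete the sentence claiming 80% power in each group. In its place:

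- State the within-group effects detectable with 80% power at N = 1044, labelled as unadjusted: Latinx 0.22, Black 0.46, Asian 0.48, White 0.58. If adjustment is credited, add adjusted values under a stated and justified correlation, and keep the unadjusted values for PoC-OP.
- Preferably, state the power of the omnibus race and ethnicity interaction as a range with the assumed effects beside each figure, and the detectable site interaction (about 0.35 SD unadjusted, 0.30 at an assumed correlation of 0.5). Language (Goal 3) has no power statement either and could be treated the same way.
- Say that subgroup and interaction results will be reported as estimates with confidence intervals, and that a non-significant interaction will not be read as equal effects.

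The cost is SAP wording and a less favourable stated power. No extra participants are needed, and the primary analysis and overall power statement do not change.

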In the event that a participant endorses Items 4 and 5 of the Paykel Suicidality Screener (see above), the CHW or CRC administering the assessment will follow the Emergency Protocol. The protocol calls for an assessment by the local emergency services. The research team member will follow up with the participant within 24 hours. If the person is admitted to emergency psychiatric services, the research team member will follow up with the participant after 30 days. If the participant no longer reports suicidality, he/she will be allowed to continue to the study. In no case will a participant with elevated symptoms be removed from the study without ensuring an appropriate referral. If a participant scores in the severe range on the PHQ-9 or the GAD-7 (corresponding to scores of greater or equal to 20 on the PHQ-9 or greater or equal to 15 on the GAD-7) for two or more assessments, that participant will be monitored closely and the CHW's supervisor will determine whether that individual should be referred to specialty treatment. Depending on the nature of the treatment, the participant may be allowed to continue with the study. The following criteria will be used to remove a subject from the study. The participant's primary care provider will be notified if his/her symptom assessment scores remain in the severe range.

IX. Potential Benefits

A. Potential benefits to participating individuals

In terms of efficacy, it is hoped that this intervention will contribute to reduced depression and/or anxiety among a significant proportion of study participants. Depressive and anxiety symptoms from baseline will be measured by the Hopkins Symptom Checklist-25, the PHQ-9, and the GAD-7, and disability days as measured by the WHO-DAS 2.

B. Potential benefits to society (e.g. increased understanding of disease process, etc.)

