The emergency procedure is prompted if a patient endorses a 4 or 5 on the Paykel suicidality screener over the last 30 days. The questions include: “Has there been a time in the last 30 days/since the last assessment when you reached the point where you seriously considered taking your own life, or perhaps made plans how you should go about doing it?” = yes or “Has there been a time in the past 30 days/since the last interview when you made an attempt on your own life?” = yes.

- 1) At the end of the session or interview, study staff should inform the participant: *“I am not a clinician; however, when anyone tells us they’ve been feeling this way recently, we connect them with a clinician who can ask some questions about how you’ve been feeling. We will also contact your primary care doctor to let them know about this conversation and make sure you are safe. We want to ensure your safety, so let me connect you right now. Could you please tell me where you are located right now?”*

2) **Study staff should immediately connect the patient to the correct Emergency Services provider** for assessment.

- Place the patient on hold (or have them wait a moment when in person).
- When speaking to emergency services team, refer to the study: I have a patient on the line as part of the research study who scored high on a suicide screening tool. I am not a clinician, and am hoping the patient can be assessed for risk by phone -- he/she has given consent to this as part of the study.
- Take the name of the person who you are talking to.
- The emergency services provider will need the following information from you:
 - patient's name
 - phone number
 - present location
 - what was said by patient re: suicidality
- If a Spanish, Mandarin, or Cantonese speaking clinician is not readily available, study staff are allowed to translate only in the capacity of informing the patient of what the emergency services provider says are the 'next steps' (i.e., someone is going to call you back in 5 minutes, etc.)

If for some reason, the participant is not able to be or refuses to be connected right away you should:

- 1) Provide the patient with the emergency services contact number, depending on where they are located.

2) Contact the emergency services provider based on where the patient is located and share the pertinent information as described above. Immediately inform the study PI and your supervisor.

Emergency Protocol Documentation Form

Patient ID #: _____

Date: _____

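### Section VIII words the suicide emergency trigger as Paykel items 4 and 5, while the sample emergency protocol acts on 4 or 5; Section VIII should say or (minor safety wording correction)

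*Combined protocol and SAP*

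**What the plan says.** The emergency trigger appears twice in Section VIII (Risks and Discomforts) and once in Section XI.A (Sample Self-Harm/Risk Emergency Protocol).

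- Section VIII.A, first statement: "Those who endorse questions 4 and 5 of the Paykel, suggesting active suicidality, will be provided emergency care". The sentence goes on to say that this care follows the research team's emergency protocol.
- Section VIII.A, later: "In the event that a participant endorses Items 4 and 5 of the Paykel Suicidality Screener", the CHW or CRC is to follow the Emergency Protocol, which calls for assessment by local emergency services. Two follow-up steps come next in the same paragraph: "The research team member will follow up with the participant within 24 hours" and "If the person is admitted to emergency psychiatric services, the research team member will follow up with the participant after 30 days".
- Section XI.A: "The emergency procedure is prompted if a patient endorses a 4 or 5 on the Paykel suicidality screener over the last 30 days". It then writes out the two questions, each ending in a yes answer and joined by *or*. The first asks whether the person "seriously considered taking your own life, or perhaps made plans how you should go about doing it"; the second asks about a time "when you made an attempt on your own life".

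Section VI, in the rule for referring enhanced usual care participants and removing them from the control group, also gives the Paykel criterion as 4 or 5. Section XI.A is introduced as an example that would be adapted to study sites.

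**The concern.** One safety rule is written with two different logical connectives. A conjunction requires both answers; a disjunction requires either. The difference falls on participants for whom it matters: someone with serious thoughts or a plan who has not made an attempt, or someone who reports an attempt but does not endorse the planning question. Under Section XI.A both go to emergency services. Under the literal text of Section VIII neither does.

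The rule is applied by CHWs and CRCs, and the script in Section XI.A has staff tell the participant that they are not clinicians. Such staff should not have to interpret a trigger or choose between two versions of it.

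**Working it through.** No arithmetic applies, and the plan gives no figure to reproduce. The check is a comparison of the texts.

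**Step 1. What each statement requires, read literally.**

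| Participant endorses | Section VIII (*and*) | Section XI.A (*or*) |
|---|---|---|
| Item 4 only (serious consideration or plans) | not triggered | triggered |
| Item 5 only (an attempt) | not triggered | triggered |
| Both items | triggered | triggered |

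The texts agree when both items are endorsed and disagree when only one is. The rows are logical cases. They say nothing about how often each occurs, so they do not measure the size of the problem.

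**Step 2. Which version is intended.** Section XI.A is the only place that writes the questions out, and it joins them with *or* after having already said 4 or 5. The Section VI rule uses 4 or 5 as well. That rule governs referral and removal from the control group, not the emergency procedure, and its other connectives are hard to parse, so it is supporting evidence only. Together they make *or* very probably the intent.

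**Step 3. Whether Section XI.A settles the wording.** Mostly, but not fully. Both statements in Section VIII point staff to an emergency protocol, and the one in Section XI.A is the only one in the document. However, it is presented as an example for sites to adapt, and the document does not say which text prevails if the two differ. A site preparing its own version has two triggers in front of it.

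**Step 4. What can be said about numbers.** Under Section VIII.A the Paykel is given after PHQ-9 item 9 is endorsed. The document gives no rate for that item, for Paykel item 4 or for Paykel item 5. The number of participants who would endorse exactly one of the two Paykel items therefore cannot be estimated from the document.

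**The case against.** The strongest reply is that the operative text is already right. Section VIII summarises risks; the procedure itself is in Section XI.A, and it says *or* without ambiguity. To endorse questions 4 and 5 can also be read distributively, as naming the two questions that raise the alarm. Staff who read the whole document would probably act correctly. Other safeguards exist too: weekly clinician supervision of CHWs with enquiry about safety (Section VIII.A), and a registry that flags staff concerns about a participant's well-being (Section X.B).

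Most of this stands, and it is why the point is minor. It does not remove the need for the edit. A loose reading is possible but not assured, and the safeguards do not replace a clear trigger.

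Some stronger readings are tempting and should be resisted:

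- A reader might infer that the 24-hour contact and the 30-day follow-up are withheld from a participant who meets only the *or* trigger, because they are written under the *and* wording. The document does not support this as a separate gap. The steps follow in sequence for anyone put through the emergency protocol, and the 30-day contact depends on admission, not on which items were endorsed. It is the same *and* reading over again.
- A reader might cite the documentation form, which lists the two items on separate lines, or the screening exclusion for affirmative Paykel responses, as further proof of *or*. Neither states an emergency trigger. Separate lines on a form fit either rule, and the exclusion names neither item.

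**Conclusion.** The inconsistency is real and lies in two statements in Section VIII. Taken literally, they omit a participant who endorses only one of the two items, contrary to the sample emergency protocol. The intended rule is very probably *or*. The practical effect is probably small, and this is a minor safety wording correction.

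This rests on two assumptions: that staff work from the emergency protocol to which Section VIII sends them, and that site-adapted versions, which are not in the document, keep the *or*. Nothing suggests that a site would change it.

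A reader might go further and infer that staff apply the *and* rule, or that participants with a lone plan or attempt go without emergency care. The document gives no evidence of either. It shows a wording conflict, not a faulty procedure in the field. Sample size, endpoints and analysis are not affected.

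**What to change.** Change two sentences in Section VIII.A:

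- First statement: *Those who endorse question 4 or question 5 (or both) of the Paykel*, with the rest of the sentence unchanged.
- Later statement: *endorses Item 4 or Item 5 (or both)*, with the rest unchanged. The trigger and the follow-up steps after it then plainly cover the same participants as Section XI.A.

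The cost is two wording edits, an IRB amendment and one staff notice. No statistical section changes.
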